7.0 Study Endpoints*

PROTOCOL TITLE: Optimization of 25(OH) vitamin D levels in African Americans

Primary Endpoints: Blood levels of 25(OH)VD, TNF- α , and HOMA-IR.

Safety Endpoints: Serum calcium (Ca²⁺), PTH, liver, and kidney function tests will be carried out at visits 0, 2, 4, and 6. Whole blood CBC and pregnancy tests will be done at all visits.

Secondary Endpoints: Blood levels of 1,25(OH)₂VD, HbA_{1c}, and pro-inflammatory and anti-inflammatory cytokines (such as IL-2, IL-6, and IL-10).

We will also perform tests to monitor liver and kidney function tests at each visit and complete blood count analyses for any sign of any anemia or unexpected changes in white or red blood cell profiles.

8.0 Procedures Involved*

Fasting blood will be drawn after an overnight fast into pre-cooled tubes kept in an ice bucket: 2 mL in a tube without anticoagulant (for the chemistry profile), 1 mL each EDTA-blood for HbA_{1c} and 1 mL for CBC, 8 mL for isolation of plasma, and 12 mL for PBMC isolation. Samples will be transported in an ice-bucket. EDTA-blood will be centrifuged, and the clear plasma saved in several aliquots for various assays. The plasma will be stored at -80°C. Information on age, height, body weight and records of any medication use will be collected from each patient at the time of enrollment. HbA_{1c}, CBC, and blood chemistry profile for glucose, Ca⁺⁺, liver, and kidney function tests, and pregnancy tests will be done at the clinical chemistry labs of LSUHSC-Shreveport. Frozen aliquots stored at -80°C will be used for all assays. Appropriate control and standards will be used, and analyses will be done in duplicate for each sample. This will eliminate inter-assay variability.

PBMC isolation and PCR studies: PBMC will be isolated using Histopaque (Sigma-Aldrich catalog # 10771) from EDTA -blood as described in our previous publications. We will assay GSH and VD metabolism genes in PBMC as described in our earlier studies.

25(OH)VD and 1,25(OH)₂VD assays: We have already standardized tests for simultaneous determinations of total 25(OH)VD and 1,25(OH)₂VD in human plasma using UPLC-MS/MS.

Whole blood total GSH, L-cysteine, will be determined using HPLC, and a whole blood Glucose-6-Phosphate Dehydrogenase (G6PD) Activity Assay Kit (Sigma, Cat # MAK015); TNF- α will be determined using an ELISA kit from R&D Systems (Minneapolis, MN). Insulin will be determined using ELISA kits from ALPCO Diagnostics (Salem, NH), and the HOMA insulin resistance index will be calculated (136). IL-2, IL-6, and IL-10 will be determined using ELISA kits from R&D Systems (Minneapolis, MN). All appropriate controls and standards as specified by the manufacturer's kits will be used; control samples will be analyzed each time to check the variation from plate to plate on different days to reduce the variability of assays. All of the analyses will be done in duplicate on each sample.

Total 24 mL blood will be collected (2 mL in a tube without anticoagulant (for the chemistry profile), 1 mL each EDTA-blood for HbA_{1c} and 1 mL for CBC, 8 mL for isolation of plasma, and 12 mL for PBMC isolation).

9.0 Data and Specimen Banking*

Plasma will be separated from blood. Aliquots of plasma stored at -80°C and will be used for all assays. Appropriate control and standards will be used, and analyses will be done in duplicate for each sample. Data on each subject will be stored in computer and will be protected by a password.

PROTOCOL TITLE: Optimization of 25(OH) vitamin D levels in African Americans

10.0 Data Management* and Confidentiality

Analyses of data will be performed by the biostatistician, [name]. A *p*-value of less than 0.05 for a statistical test will be considered significant. Data will be analyzed statistically to compare the 4 groups at baseline and various visits using ANOVA. The Wilcoxon signed-rank or paired *t*-test will be used to determine significant changes after supplementation for each treatment group, and the ANOVA test to compare the 4 treatment groups on changes. The results for the pairwise comparisons among the 4 time points will determine whether there is a significant change in the outcome variables over time. The effect of covariates or possible confounders (age, sex, BMI, initial levels of outcomes, etc.) will be controlled for and tested for their significant effects by including them in the repeated measures model used.

Based on animal studies, co-supplementation with LC+VD will be more successful and raise serum 25(OH)VD levels by nearly 30 ng/mL(17, 18). Our goal is to raise circulating 25(OH)VD levels by an average of 30 ng/mL, and reduce IR levels by 35% in all AA subjects receiving combined VD+LC supplementation. To observe a significant response or change, a sample size of 7 for 25(OH)VD, and 27 for IR were considered adequate using a paired *t*-test conducted at 5% level of significance and 80% power. We chose a goal of 30 subjects in each group who complete the study in the VD+LC supplementation and other groups. Based on our experience from a previously completed clinical trial (H-09-073), enrollment of and consent from 160 AA volunteers who participate in blood collection for screening should give us more than the required sample size of 30 subjects in each group (120 in 4 groups) after factoring in a dropout rate of about 16% for screen failures, withdrawal before randomization, or those who did not complete all the visits. Our experience also suggests that nearly 190 subjects will need to be contacted to achieve our goal of 160 AA volunteers who complete the written consent form and are enrolled in this clinical trial. This takes into account the fact that only about 85% of those initially contacted will indeed show up for the screening visit and complete the written informed consent.

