1.0 Objectives*

Two-thirds of the US population, particularly African Americans (AA), is at risk for inadequate or deficient 25-hydroxy-vitamin D (25(OH)VD). Epidemiological studies demonstrate an association between better health outcomes and higher blood levels of 25(OH)VD. Randomized controlled clinical trials have shown that, while supraphysiological high doses of VD are needed to achieve adequate blood levels of 25(OH)VD, not all subjects respond to them. Recent studies have also questioned the therapeutic effects of high-dose VD supplementation. This application presents our design for a randomized, double-blind, placebo-controlled clinical trial to test the hypothesis that supplementation with VD in combination with L-cysteine (LC) is more successful at optimizing the statuses of 25(OH)VD [biological signatures] and simultaneously decreasing TNF- α and IR [functional or clinical outcomes], suggesting a better therapeutic approach compared with supplementation with VD alone in AA subjects.

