2.0 Background*

Previous human studies report that VD supplementation increases circulating 25(OH)VD status but has limited success in reducing insulin resistance (IR). Other human studies report that supplementation with LC lowers TNF- α and IR. This clinical trial will determine the impact of combined supplementation with VD+LC on increases in levels of 25(OH)VD as well as simultaneous reduction in TNF- α and IR biomarkers (mediators of clinical benefit) in the AA population. The mechanistic focus of this clinical trial will determine whether combined supplementation with VD and LC provides a more successful approach to increasing 25(OH)VD [biological signatures] as well as simultaneously decreasing TNF- α and IR [functional or clinical outcomes], compared with supplementation with VD alone. If the results are positive, future studies will investigate potential of this approach to reduce the inflammation, pain, and other health issues among AA in a full-scale efficacy trial.

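### The protocol hypothesizes that VD+LC beats VD alone, but its analysis section names no VD+LC versus VD comparison and its sample size is for within-arm change

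*Protocol*

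**What the plan says.** **Hypothesis.** Protocol section 1.0 says the combination should raise 25(OH)VD and lower TNF-α and IR together, "suggesting a better therapeutic approach compared with supplementation with VD alone in AA subjects". Section 2.0 repeats the aim with the same comparator: a rise in 25(OH)VD "as well as simultaneous reduction in TNF"-α and IR.

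**Endpoints.** Section 7.0 lists "Primary Endpoints: Blood levels of 25(OH)VD", TNF-α and HOMA-IR, without ranking them.

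**Tests.** Section 10.0 states that a *p* "value of less than 0.05 for a statistical test will be considered significant". It then lists:
- an analysis "to compare the 4 groups at baseline and various visits using ANOVA";
- a signed-rank or paired *t*-test of change within each arm;
- "the ANOVA test to compare the 4 treatment groups on changes";
- a statement that "pairwise comparisons among the 4 time points will determine whether there is a significant change";
- a repeated measures model, mentioned only as the place where covariates are included.

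**Sample size.** Section 10.0 gives n = 7 for 25(OH)VD and n = 27 for IR from a paired *t*-test at the 5% level with 80% power. The targets are changes in the VD+LC arm: +30 ng/mL and -35%. The goal is 30 completers per arm. No SD, sidedness or TNF-α figure is given.

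**The concern.** The hypothesis concerns one contrast, VD+LC against VD, on three endpoints together. No listed test is tied to that contrast. The ANOVAs ask whether any of the four arms differ, the paired tests ask whether an arm changed from its own baseline, and the only pairwise comparisons named are between times, not arms.

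This matters because section 2.0 says: "Previous human studies report that VD supplementation increases circulating 25(OH)VD status but has limited success in reducing insulin resistance". If VD alone raises 25(OH)VD, the two VD-containing arms will differ from the other two, and the VD+LC arm will change from baseline, even if L-cysteine contributes nothing. Both results would be significant by the section 10.0 criterion, and either could be reported as support for the combination. The stated 80% power likewise belongs to a within-arm question that the hypothesis does not ask.

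**Working it through.** **Inputs.** From section 10.0: 30 completers per arm; paired *t*-test, 5% level, 80% power; n = 7 for +30 ng/mL; n = 27 for -35% IR. Assumed, because the protocol gives no values: the effect of VD alone on 25(OH)VD (10, 15 or 20 ng/mL), equal SDs across arms, no effect of VD alone on IR, and a baseline/follow-up correlation of 0.3-0.8.

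**1. The plan's own n.** With no SD given, 7 and 27 cannot be reproduced, only solved backwards. Paired *t*-test power is P(T > t_crit), with T noncentral *t* on n-1 df and noncentrality d√n. The smallest n reaching 80% fixes a range for d:

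| Stated n | Sidedness | d | Implied SD of change |
|---|---|---|---|
| 7 | two-sided | 1.273-1.435 | 30/d = 23.6-20.9 ng/mL |
| 7 | one-sided | 1.067-1.186 | 30/d = 28.1-25.3 ng/mL |
| 27 | two-sided | 0.560-0.572 | 35/d = 62-61 percentage points |
| 27 | one-sided | 0.491-0.501 | 35/d = 71-70 percentage points |

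The SD of change in 25(OH)VD is therefore 20.9-28.1 ng/mL.

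**2. Four-group ANOVA on 25(OH)VD change when L-cysteine adds nothing.** Arm means are (0, 0, δ, δ) for placebo, LC, VD and VD+LC. The grand mean is δ/2, so the noncentrality is λ = 30 × 4 × (δ/2)²/SD² = 30δ²/SD². Power is P(F(3,116; λ) > 2.683). Example: δ = 10, SD 20.9 gives λ = 3000/436.8 = 6.87 and power 56%; SD 28.1 gives λ = 3000/789.6 = 3.80 and power 33%.

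| Assumed VD effect | SD 28.1 | SD 23.6 | SD 20.9 |
|---|---|---|---|
| 10 ng/mL | 33% | 46% | 56% |
| 15 ng/mL | 67% | 83% | 92% |
| 20 ng/mL | 91% | 98% | 99.6% |

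**3. Other tests in the same situation.** The paired test within the VD+LC arm (noncentrality δ√30/SD, SD 23.7) is significant in 61%, 92% and 99% of trials for δ = 10, 15 and 20. In 4,000 simulated trials at each δ, a direct VD+LC versus VD *t*-test favoured VD+LC in about 2-2.5%, its nominal rate.

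**4. Between-arm power for IR, 30 per arm, tested at two-sided 0.05.** If VD leaves IR unchanged, the between-arm standardized difference in change equals d from step 1.
- Unadjusted two-sample *t* (58 df, noncentrality d√15): d = 0.560 gives 2.17 and power 57%; d = 0.491 gives 1.90 and power 46%.
- Baseline-adjusted: with equal variance σ² at both times and correlation ρ, the SD of change is σ√(2(1-ρ)) and the adjusted residual SD is σ√(1-ρ²). So d is multiplied by √(2/(1+ρ)), which is 1.054 at ρ = 0.8 and 1.240 at ρ = 0.3. On 57 df, d = 0.560 becomes 0.590-0.695, power 61-75%; d = 0.491 becomes 0.518-0.610, power 51-64%.

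The upper end of each d range adds less than two percentage points. All these values are below 80%.

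**5. 25(OH)VD between arms.** Power depends on how much VD alone achieves. At SD 23.7 the unadjusted test has 36%, 67%, 90% and 99.8% power for a VD+LC minus VD difference of 10, 15, 20 and 30 ng/mL. The stated n of 7 does not address this.

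**The case against.** **An analysis plan may supply the contrast.** A primary contrast and success rule are often left to the SAP, which is not at hand. That is fair as far as it goes. But section 10.0 is not silent: it fixes a set of tests, a criterion for significance and a basis for the sample size, and these do not address the protocol's own hypothesis. A later SAP could add the contrast without changing the printed power basis.

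**The repeated measures model could carry the contrast.** This stands. It would be too strong to infer that the planned methods cannot test the hypothesis. The protocol simply does not say that the model will be used for this.

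**The time point can be read from the text.** Change after supplementation, with six months of supplementation in section 6.0, most naturally means baseline to the end of treatment. This also stands; stating it removes the remaining doubt.

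**Type I error.** A reader might infer that a per-test 0.05 over three unranked endpoints and several visits inflates the error rate. The documents do not support that. Nowhere do they say that one endpoint, or any visit, is enough. The stress on simultaneous benefit points to all three being required, and under that rule at a fixed time point the error is at most 5% without adjustment.

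**The power figures depend on the analysis.** This stands. A reader might settle on 57% as the trial's power for IR and derive one required sample size from it. That figure is for an unadjusted test with a two-sided paired calculation. Sidedness is not stated, and section 10.0 intends adjustment for initial levels, so only a range is defensible.

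**Conclusion.** The point holds as a mismatch between the stated hypothesis and the stated tests and power basis. That part rests on the text alone.

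Its size rests on assumptions. If L-cysteine adds nothing and VD alone raises 25(OH)VD by 10, 15 or 20 ng/mL, the planned ANOVA is still significant in about 33-56%, 67-92% or 91-99.6% of trials. The ANOVA is not wrong about its own null hypothesis; it answers a different question.

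The 80% power does not carry over to VD+LC versus VD. The IR figures in step 4 assume that VD leaves IR unchanged and that SDs are equal. If VD lowers IR somewhat while the VD+LC change stays as targeted, power is lower. Power for all three endpoints jointly cannot exceed the IR power of whichever analysis is used.

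The point does not extend to a claim of inflated type I error, to a claim that 0.05 is wrong for a single test, or to one required sample size.

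**What to change.** In Protocol section 10.0, add wording such as:

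> *The primary comparison is VD+LC versus VD at the end of the 6-month supplementation, estimated from the repeated measures model adjusted for baseline level, age, sex and BMI. The hypothesis is supported only if VD+LC is better than VD on all three primary endpoints, each at two-sided 0.05. The four-group ANOVAs, within-arm changes and time-point comparisons are supportive.*

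Next to the sample size, add:

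> *The n of 7 and 27, with 80% power, apply to within-arm change only. With 30 completers per arm, power for IR, VD+LC versus VD, is below 80%: about 57% unadjusted (about 46% if the paired calculation was one-sided) and about 61-75% with baseline adjustment (baseline/follow-up correlation 0.8-0.3; about 51-64% if one-sided), assuming that VD alone leaves IR unchanged and that SDs are equal. Power for all three endpoints jointly cannot exceed the IR power of the analysis used.*

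If the sponsor still has the SDs and sidedness behind 7 and 27, these should replace the back-calculated ranges. The cost is wording, a stricter success rule and a less favourable power statement. No new data or visits are needed.

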5.0 Multi-Site Research* N/A (This is only site)

6.0 Study Timelines*

Potential subjects will be contacted over phone or potential subjects may call in response to advertisement and agrees to participate in this study will be asked to come to the clinic after fasting overnight. Fasting blood will be collected after written informed consent. Blood collected at V₋₁ will serve as the sample for the screening visit for the clinical trial. Subjects meeting the inclusion/ exclusion criteria will continue in the clinical trial. All subjects will fill out the complete standard health history before the study and at each visit during the study. This clinical trial will be registered at the ClinTrial.gov site.

Initially, all of the study subjects will be provided placebo supplementation as a placebo run-in period for one month before randomization. Visit 2 (V₀) is for obtaining baseline levels after the run-in period. AA-subjects will be block randomized into four groups. Members of the groups will ingest capsules containing placebo and supplements, orally, daily: (I) placebo (P); (II) LC (1000 mg); (III) VD (2000 IU); (IV) VD and LC. Each capsule will contain a placebo or cholecalciferol (2000 IU) or LC (1000 mg). Placebo group will take two placebo capsules a day in the morning; II LC group will receive two capsules of LC daily; (III) VD group will take two capsules and each capsule will contain 1000 IU VD daily; (IV) VD+LC group will take daily two capsule containing 1000 IU+500 mg LC. Supplements will be taken daily with food at breakfast for 6 months, while participants continue to carry on a normal lifestyle. During the placebo run-in period, all subjects will also take two placebo capsules daily. Based on previous experience, we expect a dropout rate of about 16% as a result of non-compliance, lost contact, taking another medicine, or a subject found to have another disorder. We expect that at least 30 subjects in each group will complete the study. Overnight fasting blood will be collected at each visit. Also, anthropomorphic data, body weight, and height (BMI), the record of any drug use, any adverse effects/complaints (related or unrelated), and Questionnaire will be collected at each visit by the nurse. It is likely to require ~90 minutes to collect the subject's history and other data in interviews with the nurse/dietician and investigators.

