28.0 Drugs or Devices

This research involves dispensing micronutrient supplements vitamin D and L-cysteine. These are also sold over the counter in any discount store. These nutrients are normal part of our food consumed by the public, such as milk, cheese, eggs and green vegetables. The supplement capsules will be provided by the investigators free of any cost to the participants.

Capsules details.

1. The study subjects will ingest capsules containing placebo and supplements, orally, daily: (I) placebo (P); (II) L-cysteine (LC) (1000 mg); (III) Vitamin D (VD) (2000 IU); (IV) VD+LC groups
2. To start with each group/subject will have placebo run-in period for one month and all subjects will take two placebo capsules daily.
3. After one month of Placebo run-in period, all subjects will be randomized into four groups. Each capsule will contain a placebo or cholecalciferol (2000 IU) or LC (1000 mg) or VD+LC. Supplements will be taken daily with food at breakfast for 6 months.
4. Placebo group will take two placebo capsules a day in the morning; II LC group will receive two capsule of LC (500 mg each) daily; (III) VD group will take two capsule of VD (1000 IU) daily; (IV) VD+LC group will take daily two capsule of combination (VD 1000 IU VD+ 500 mg LC) daily.
5. Supplements will be taken daily with food at breakfast for 6 months.
6. We are working with Company named: Superior Supplement Manufacturing, Fountain Valley California, to get these capsules made. These capsules will look similar and will be of similar size.

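### The four arms form a VD-by-LC 2x2, but section 10.0 states only four-group ANOVAs and within-arm tests, so no stated test isolates what LC adds

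*Protocol*

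**What the plan says.** Section 6.0 of the protocol lists the arms as "I) placebo (P); (II) LC (1000 mg); (III) VD (2000 IU); (IV) VD and LC" and states that "AA-subjects will be block randomized into four groups". The primary endpoints in section 7.0 are "Blood levels of 25(OH)VD, TNF- α , and HOMA-IR". Sections 1.0 and 2.0 put the question as whether VD with LC does better than VD alone.

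For comparisons between arms, section 10.0 says "Data will be analyzed statistically to compare the 4 groups at baseline and various visits using ANOVA", and adds an ANOVA of the four arms on changes. Its other stated tests are paired tests within each arm and comparisons between time points. It also mentions a repeated measures model with covariates but does not describe the treatment terms. The sample size comes from a paired t-test within an arm. The protocol nowhere mentions a factorial design, a main effect, an interaction or a named contrast between arms.

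On capsule content, section 28.0 (item 4) says "II LC group will receive two capsule of LC (500 mg each) daily" and "VD+LC group will take daily two capsule of combination (VD 1000 IU VD+ 500 mg LC) daily". Section 6.0 says "Each capsule will contain a placebo or cholecalciferol (2000 IU) or LC (1000 mg" and gives the LC arm two LC capsules a day. Item 3 of section 28.0 repeats the per-capsule amounts of section 6.0.

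**The concern.** The scientific question is what LC contributes when it is added to VD. A test that four means are equal can be significant because VD raises 25(OH)VD over placebo, and it then says nothing about LC. Conversely, an LC effect is diluted when it is spread over three degrees of freedom.

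The design offers more. Section 2.0 reports that LC by itself lowers TNF-alpha and IR, and that "VD supplementation increases circulating 25(OH)VD status but has limited success in reducing insulin resistance (IR". If LC acts on these two primary endpoints whether or not VD is given, the LC versus placebo comparison carries the same information as VD+LC versus VD, and the two can be combined. The interaction would estimate whether LC works differently in the presence of VD, which is the mechanistic question. No stated analysis targets any of these quantities.

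**Working it through.** **Is it a 2x2?** On item 4 of section 28.0, the LC arm takes 2 x 500 = 1000 mg of LC a day. The combination arm takes 2 x 1000 = 2000 IU of VD and 2 x 500 = 1000 mg of LC. These equal the daily amounts listed for the single arms, so all four cells are present. On the per-capsule figure of section 6.0, two LC capsules would be 2 x 1000 = 2000 mg a day, and the two LC arms would not match.

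**Inputs.** 30 completers per arm, 120 in total (section 10.0). 5% level, taken as two-sided because the protocol does not say. Stated n = 27 for IR with a paired t-test at 80% power. Equal allocation, inferred from the goal of 30 per group.

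**The plan's own figure.** n = 27 cannot be reproduced, because no SD is given. Solved backwards with the noncentral t, it implies a standardised within-arm change of 0.56 to 0.57. I use d = 0.56 SD as an assumed between-arm LC effect. This is a borrowed figure. The protocol gives no between-arm effect, and no planning figure at all for TNF-alpha.

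**Formulas** (pooled error, 4 x 30 - 4 = 116 df; r is the LC effect without VD divided by the LC effect with VD):
- VD+LC versus VD: noncentrality d / sqrt(2/30) = 0.56 / 0.258 = 2.17. Power 58% (57% with the two arms' own 58 df).
- Four-group ANOVA, r = 1, no VD effect: noncentrality 30 x 4 x 0.28^2 = 9.41 on 3 and 116 df. Power 72%.
- LC main effect, 60 versus 60: noncentrality d(1 + r)/2 / sqrt(1/30). At r = 1 this is 0.56 / 0.183 = 3.07. Power 86%.
- Interaction: noncentrality d(1 - r) / sqrt(4/30). At r = 0 this is 0.56 / 0.365 = 1.53. Power 33%.

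**Dependence on r, at d = 0.56 SD:**

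| LC effect without VD | VD+LC vs VD | Four-group ANOVA | LC main effect | Interaction test |
|---|---|---|---|---|
| same (r = 1) | 58% | 72% | 86% | no interaction |
| half (r = 0.5) | 58% | 54% | 63% | 12% |
| none (r = 0) | 58% | 58% | 33% | 33% |

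The ANOVA noncentralities in rows two and three are 30 x 0.2156 = 6.47 and 30 x 0.2352 = 7.06, where the second factor is the sum of squared deviations of the four means.

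**Break-even.** The main effect beats the pairwise contrast when (1 + r)/2 > 1/sqrt(2), that is r > sqrt(2) - 1 = 0.41.

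**Range over d, with r = 1** (pairwise / ANOVA / main effect):
- 0.30 SD: 21 / 24 / 37%
- 0.40 SD: 34 / 41 / 58%
- 0.50 SD: 48 / 61 / 78%
- 0.70 SD: 77 / 90 / 97%

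**The case against.** The best reply is that section 10.0 does not say one-way. A two-way ANOVA also compares four groups, a one-way fit carries the same cell means, and the coding and contrasts may sit in an analysis plan that is not shown. This stands in part. It rules out saying that the trial treats the arms as unrelated groups or will never estimate an interaction. It leaves the narrower point intact: the protocol does state its between-arm and within-arm tests, and none of them targets the comparison it sets out to make.

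Three stronger readings are tempting, and the documents do not support them.
- *The placebo and LC arms are wasted.* They are not. A four-group ANOVA uses all 120 completers, and its 72% depends on them.
- *Much power is lost.* Against the ANOVA that section 10.0 names, the gap at 0.56 SD is 86 - 72 = 14 points. The larger gap of 86 - 58 = 28 points is against a pairwise test that the section does not describe. Both hold only without interaction.
- *VD has little effect on IR, so LC must act alike with and without VD.* This does not follow. A small VD effect says nothing about interaction. The statement in section 2.0 that LC itself lowers TNF-alpha and IR makes an LC effect without VD plausible, but it does not fix its size, and the trial's premise is that the combination works better.

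It is also fair to say that the main effect is a different estimand. Reporting it leaves the VD+LC versus VD hypothesis at about 58%.

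**Conclusion.** The point holds in a limited form. The arms form a VD-by-LC 2x2 on the amounts in item 4 of section 28.0, and the stated tests neither use that structure nor isolate what LC adds. Naming the contrast gives the hypothesis a test of its own. Using the factorial structure adds a supporting LC estimate for HOMA-IR and TNF-alpha, with 86% power against 72% for the four-group ANOVA at 0.56 SD if there is no interaction. That advantage shrinks to 63% against 54% at half effect, and it reverses to 33% against 58% if LC works only together with VD.

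The trial cannot settle by a test which of these cases it is in, since the interaction test has 33% power even for full synergy. All these figures rest on 30 completers per arm, a two-sided 5% level, equal variances, no VD effect in the ANOVA calculation, and an effect size borrowed from a within-arm change. The conflict over LC content per capsule is a separate condition: without the same LC amount in both LC arms, the pooled estimate has no clear meaning.

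**What to change.** Before unblinding:

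1. Code the ANOVA on changes and the repeated measures model with terms for VD, LC and VD x LC.
2. Name VD+LC minus VD as the contrast that tests the stated hypothesis, for all three primary endpoints.
3. For HOMA-IR and TNF-alpha, also report the LC main effect (both LC arms versus both others) as a pre-specified supporting estimate, and say that its gain is conditional on LC acting alike with and without VD. For 25(OH)VD, where interaction is plausible, keep to the simple contrast.
4. Report the interaction with its 95% CI as an estimate. Do not use its p-value to decide whether to pool.
5. Reconcile sections 6.0 and 28.0 on the LC content per capsule in the LC arm, and state whether the two LC arms receive the same daily amount.

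The cost is recoding one model and adding a few sentences of text, with no new subjects or measurements. The change does not repair the power of the VD+LC versus VD comparison, which depends on the sample size and not on the coding.

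### Section 10.0 tests the group difference by two unadjusted ANOVAs and, by implication, an adjusted model, each at p<0.05 with none deciding, so the false-positive rate can reach roughly 9% to 10%

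*Protocol*

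**What the plan says.** Section 7.0 lists three primary endpoints: "Primary Endpoints: Blood levels of 25(OH)VD, TNF- α , and HOMA-IR". Section 10.0 sets one rule for all tests: "A *p*-value of less than 0.05 for a statistical test will be considered significant". The same paragraph then describes these analyses that bear on the difference between arms:

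- **Levels:** "Data will be analyzed statistically to compare the 4 groups at baseline and various visits using ANOVA".
- **Changes:** "the ANOVA test to compare the 4 treatment groups on changes".
- **Adjusted model:** covariates, among them the starting value of each outcome, "will be controlled for and tested for their significant effects by including them in the repeated measures model used".

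The paragraph gives no order among the three. Its one sentence about what will determine a conclusion concerns change across the four time points, not the difference between arms. No other section of the protocol names a deciding analysis.

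**The concern.** Level, change and baseline-adjusted level are three estimates of the same arm effect from the same blood samples. They differ in how they treat chance imbalance at V0. For TNF-α and HOMA-IR, where a fall is wanted, an arm that happens to start high looks worse on level and better on change. For 25(OH)VD, where a rise is wanted, the same arm looks better on level and worse on change. One analysis can therefore be significant when the other is not, through baseline imbalance alone.

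Under the stated rule each result counts as significant in its own right, so a claim can rest on whichever one crosses 0.05. The 5% level then no longer describes the chance of a false claim, even after one endpoint and one visit have been fixed.

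**Working it through.** **The plan's own figure.** The protocol states 0.05 per test and no overall error rate, so there is no overall figure to reproduce.

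**Inputs from the protocol.** Four arms; 30 completers per arm ("We chose a goal of 30 subjects in each group who complete the study in the VD+LC supplementation and other groups"); 0.05 per test; the initial outcome level as a covariate.

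**Inputs assumed.** The correlation r between baseline and follow-up (0 to 0.9), normal data, and equal standard deviations at both times. Only one visit is considered, so the adjusted model reduces to an analysis of covariance on the baseline value. Age, sex and BMI are left out of the simulation.

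**Step 1: bounds.** If the tests were independent, two would give 1 − 0.95² = 9.75% and three would give 1 − 0.95³ = 14.3%. The tests are correlated, so the true figures lie below these.

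**Step 2: simulation with no treatment effect.** 40,000 trials per row, 4 × 30 subjects, each F-test at 0.05.

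| r | Level | Change | Adjusted | Either ANOVA | Any of three |
|---|---|---|---|---|---|
| 0 | 0.049 | 0.052 | 0.049 | 0.085 | 0.087 |
| 0.3 | 0.052 | 0.051 | 0.051 | 0.092 | 0.097 |
| 0.5 | 0.050 | 0.048 | 0.049 | 0.091 | 0.097 |
| 0.7 | 0.049 | 0.050 | 0.049 | 0.093 | 0.102 |
| 0.8 | 0.050 | 0.050 | 0.050 | 0.096 | 0.105 |
| 0.9 | 0.050 | 0.050 | 0.050 | 0.096 | 0.104 |

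Each test alone holds its 5%. The excess comes from having several chances.

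**Step 3: how often the two ANOVAs disagree.** The probability that exactly one is significant is 2 × P(either) − P(level) − P(change). At r = 0.5, with unrounded inputs, this is 2 × 0.0905 − 0.0502 − 0.0480 = 0.083. At r = 0.7 it is 2 × 0.0929 − 0.0493 − 0.0496 = 0.087. So nearly all of the either-ANOVA rate is one ANOVA significant without the other.

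**Step 4: sensitivity of the any-of-three rate.** The first two lines use r = 0.3, 0.5 and 0.7; the third uses r = 0.3 to 0.9.

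- Follow-up SD relative to baseline SD: 10.2% to 11.7% at 0.75 times, 8.8% to 9.2% at 1.25 times, 8.2% to 8.6% at 1.5 times, 7.6% to 8.9% at 2 times.
- Lognormal data: 8.8% to 9.9%.
- Adjusted model pooling three post-baseline visits: 11.7% to 12.5% if the group effect is read, 12.5% to 13.7% if the group-by-time effect is read.

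**Step 5: precision.** With the level analysis set to 1, the large-sample variance of an arm difference is 2(1 − r) for change and 1 − r² for the baseline-adjusted analysis.

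| r | Level | Change | Adjusted |
|---|---|---|---|
| 0.3 | 1 | 1.4 | 0.91 |
| 0.5 | 1 | 1.0 | 0.75 |
| 0.7 | 1 | 0.6 | 0.51 |

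The adjusted analysis has the smallest variance in every row.

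**The case against.** **Choosing the deciding analysis can be left to the statistical analysis plan.** This is the strongest objection, and an unseen plan may well name one. But the point is not that detail is absent. The protocol itself states two group tests of the same comparison and a rule that makes each of them significant at 0.05. A later plan would have to override that text.

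**The third test is not explicit.** This stands. The sentence on the repeated measures model speaks of controlling for and testing covariates; that the model also tests the arms is implied. The conclusion does not depend on it, since the two explicit ANOVAs alone give about 8.5% to 9.6%.

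**The rate depends on assumptions.** This also stands. A reader might infer that the protocol doubles its error rate as a matter of fact. The documents do not support that: they give neither the correlation nor the ratio of standard deviations, and nowhere say that any single significant result will be claimed as a group difference. They only leave room for it.

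**Opposite verdicts.** A reader might infer that level and change could point in opposite directions, both significantly. For a two-arm contrast with equal standard deviations and no effect, the two statistics are positively correlated, at √((1 − r)/2). By the bivariate normal distribution, opposite significant results then occur in about 0.001% of trials at r = 0.5 and 0.01% at r = 0.8. The realistic conflict is significant against non-significant.

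**Levels or changes.** A reader might also take the words on blood levels in section 7.0 as choosing level over change. They name the analytes. The goals and sample size in section 10.0 are framed as changes, so the protocol does not settle the matter either way.

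**Conclusion.** The point holds in a limited form. Section 10.0 offers two explicit unadjusted tests of the group difference and one implied adjusted test, each significant at 0.05, with no order among them. If any significant result is read as a group difference, the false-positive rate for one endpoint at one visit is roughly 9% to 10% (8.7% to 10.5% in the simulation, for correlations of 0 to 0.9 and equal standard deviations). It is lower, about 7.6% to 8.9%, if the follow-up standard deviation is double the baseline one, and higher if the adjusted model pools several visits. Under every assumption tried it exceeds 5%. The loss of error control is moderate and cheap to remove, so the text should be changed. It is separate from multiplicity across the three primary endpoints.

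**What to change.** In section 10.0, state that the between-arm conclusion for each primary endpoint rests on the group effect from the repeated measures model already planned, adjusted for the V0 value, age, sex and BMI. Name one visit and one contrast for that conclusion, for example VD+LC versus VD at the final visit, which matches the hypothesis in section 1.0. Without a named visit and contrast, the one model would still yield several tests. Label the unadjusted ANOVAs of levels and of changes as descriptive.

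The cost is a few sentences, with no extra subjects, samples or assays. The downside is that a significant unadjusted ANOVA can no longer support a claim by itself when the adjusted comparison is not significant. The change restores 5% for each primary endpoint separately; it does not deal with having three of them, which needs its own rule.
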